4.1.6.4 Rationale for Choice of Study Population

This study plans to enroll participants with RMS who have an EDSS score of 0–5.5 at screening and who have had 2 documented clinical attacks within the previous 2 years or 1 clinical attack that occurred within the last year before screening. These criteria have been implemented to further characterize the benefits of treatment with ocrelizumab in a wide range of participants with RMS with varying degrees of disease activity and severity.

The age range will be limited to ≤ 55 years to avoid confounding by neurological conditions prevalent in older individuals, including but not limited to, microvascular disease.

Exclusion of participants in whom Rebif has failed or who cannot tolerate Rebif prevents these participants from being randomized to further Rebif therapy and reduces the potential for unbalanced dropout rates. Additional exclusion criteria relating to concomitant diseases, laboratory parameters, and previous medications help to ensure participant safety in the study. See Section 5.3 for more details.

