2.3 DETERMINATION OF SAMPLE SIZE

The sample size for this study was estimated on the basis of data from previous RRMS trials, with use of two-sided tests with an experiment-wise alpha of 0.05. The ARR at 96 weeks in patients receiving ocrelizumab is predicted to be 0.165 (SD of approximately 0.60), compared with 0.33 (SD of approximately 0.80) in patients receiving the control treatment (interferon beta-1a 44 µg SC); this represents a relative reduction of approximately 50% with ocrelizumab treatment compared with the active comparator. For the ARR, a t-test was used to determine the sample size between ocrelizumab and interferon beta-1a 44 µg SC. The sample size of 400 patients per treatment group provides 84% power, maintaining the type I error rate of 0.05 and with the assumption of a dropout rate of approximately 20% (with the assumption that relative reduction among patient dropout is 25%).

For confirmed disability progression, a two group test of equal exponential survival with exponential dropout was used to determine the sample size. Assuming the 2-year confirmed disability progression rate is 18% for the interferon beta-1a 44 µg SC arm and 12.6% for the ocrelizumab arm (this represents a relative reduction of 30% on ocrelizumab compared to the active comparator), and assuming a dropout rate of 20% over 2 years approximately, the sample size of 400 per arm will provide 80% power,

maintaining the type I error rate of 0.05 based on the pooled analysis of two RMS studies (800 patients treated with ocrelizumab 600 mg and 800 patients treated with interferon beta-1a 44 µg SC).

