As a sensitivity analysis, the primary analysis negative binomial model described above will be adjusted by the following additional covariates: number of relapses occurring within the 2 years prior to study entry, baseline presence of Gd lesions (present or absent), prior MS treatment, and age (<40, ≥40).

A Poisson model with the same covariates as the primary analysis negative binomial model will be fitted.

Three further sensitivity analyses will be undertaken:

- The annualized protocol-defined relapse rate at Week 96 will be calculated including all protocol-defined relapses occurring during the 96-week, double-blind, double-dummy phase or the SFU Phase, up to 96 weeks after randomization. In this analysis, the exposure time will be calculated as follows:

$$\text{Exposure Time} = ((\text{Date of Week 96 visit or date of last visit up to 96 weeks after randomization}) - \text{date of study Day 1} + 1) / 365.25$$

- A sensitivity analysis for the annualized protocol-defined relapse rate at Week 96 using multiple imputations will be performed to explore the potential influence of informative dropouts on the results of the primary efficacy analyses. The multiple imputations will be used to impute the events for patients who discontinued treatment early during the 96-week, double-blind, double-dummy phase without any protocol-defined relapse during the 30 days prior to discontinuation of study treatment. Multiple imputation inference involves three distinct phases:
 1. The missing data are filled in “m” times to generate “m” complete data sets. Instead of filling in a single value for each missing value, multiple imputation replaces each missing value with a set of “m” plausible values that represent the uncertainty about the right value to impute.
 2. The “m” complete data sets are analyzed using standard statistical analyses.
 3. The results from the “m” complete data sets are combined to produce inferential results.

In this analysis, 50% of the patients who discontinued treatment early during the 96-week, double-blind, double-dummy phase without any protocol-defined relapse during the 30 days prior to discontinuation of study treatment will be randomly assigned to have an event at the date of treatment discontinuation; the other 50% of these patients will be censored at the date of treatment discontinuation. A total of 1000 (m = 1000) imputed datasets will be produced.

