The primary model described in the “Analysis Methods” section above will be applied to each of the imputed datasets. Each imputed dataset will produce an estimate of the difference between ocrelizumab and interferon beta-1a 44 µg SC. The multiple imputation estimator of the difference between ocrelizumab and interferon beta-1a 44 µg SC is the average of the individual 1000 estimators. The variance of the estimator is the combination of the between- and within-imputation variability ([Carpenter and Kenward 2007](#)).

- The annualized protocol-defined relapse rate at Week 96 will be calculated such that patients who discontinued treatment early during the 96-week, double-blind, double-dummy phase without any protocol-defined relapse during the 30 days prior to discontinuation of study treatment will be counted as having had a relapse on the date of treatment discontinuation. This approach is similar to above, but here the described approach is applied to 100% of such patients (hence no imputation), rather than randomly to 50% of such patients (with multiple imputation).

OLE Phase

The annualized protocol-defined relapse rate as defined above will be calculated for every year from Study Day 1 and from the start of the OLE period (Year 3).

Each yearly interval will be defined as the follows,

- Year 1: Treatment start date up to -1 day before Week 48; if WEEK 48 is missing then take the minimum of treatment start date+48*7 or treatment end date as the last day
- Year 2 (only exists if treatment end date is strictly after the last day of Year 1): Year 1 end date+1 up to either OLE start date if it is available, or the treatment end date
- Year 3 (only exists if OLE start date is not missing and OLE end date is strictly after the last day of Year 2): Year 2 end date+1 up to 1 day before OLE Week 48; if OLE Week 48 is missing then take the minimum of (OLE start date+48*7 or OLE end date or last known alive date as the last day).
- Year 4: Similar to Year 3 but from OLE Week 48+1 up to 1 day before OLE Week 96.
- The subsequent years will be similar to Year 4 definition with addition of 48 weeks for yearly interval.

So, ARR will be calculated and presented at every 48 weeks interval.

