Time to confirmed disability progression in the ocrelizumab group and in the interferon beta-1a 44 μg SC group will be compared using a two-sided log-rank test stratifying by geographical region (United States vs. ROW), and baseline EDSS (< 4.0 vs. ≥ 4.0). The proportion of patients with confirmed disability progression will be estimated using Kaplan-Meier methodology. A by-treatment Kaplan-Meier plot will be presented for this endpoint. The overall hazard ratio will be estimated using a stratified Cox regression model with treatment group as covariate and the same stratification factors used in the stratified log-rank test above.

Sample SAS code can be found below (SAS code is regarded as “draft” until fully validated at the analysis stage):

```
* Log-rank test;
proc lifetest data=CDP12;
  time CDP12TIME*CNSR(1);
  strata REGION BEDSSCAT / group=ARMCD;
  ods output HomTests =_logrank;
run;
```

```
* Cox regression model;
proc phreg data=CDP12;
```

```
class ARMCD / descending;  
model CDP12TIME*CNSR(1) = ARMCD / rl;  
strata REGION BEDSSCAT;  
ods output ParameterEstimates=est;  
run;
```

The analysis described above will be repeated for the per-protocol population as a sensitivity analysis.

Additionally, the following sensitivity analyses will be performed:

- Use of two different methods for handling of missing data:

Method 1: with use of the same kind of multiple imputation approach described at the end of Section 4.4.1, patients with an initial disability progression during the 96-week, double-blind, double-dummy treatment period who discontinue the treatment early and do not have a subsequent visit with EDSS measurement will be randomly imputed as an event of confirmed disability progression at the date of initial disability progression with a probability of 50%; the other 50% of these patients will be censored at the date of initial disability progression. A total of 1000 ($m=1000$) imputed datasets will be produced.

Method 2: Patients with an initial disability progression during the 96-week, double-blind, double-dummy treatment period who discontinue the treatment early and do not have a subsequent visit with EDSS measurement will be imputed as an event of confirmed disability progression at the date of initial disability progression.

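### The 50% and 100% relapse-imputation rules treat both arms alike, so they respond to relative dropout and not to worse outcomes in ocrelizumab dropouts

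*SAP*

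**What the plan says.** The primary analysis (SAP 4.4.1) is a negative binomial model with a log-exposure offset, reported as a rate ratio. Exposure and relapse counting stop at early treatment discontinuation. Under the sensitivity checks, the SAP lists three further analyses:

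1. Relapses observed in the double-blind or safety follow-up phase, up to 96 weeks after randomization, with exposure extended to match. Nothing is imputed.
2. Multiple imputation, with the stated aim of exploring informative dropout. Eligible patients are early discontinuers without a protocol-defined relapse in the 30 days before stopping; they may have relapsed earlier. Half of them "will be randomly assigned to have an event at the date of treatment discontinuation" and the other half are censored there, over 1000 imputed datasets.
3. The same idea without the random half: every eligible patient "will be counted as having had a relapse on the date of treatment discontinuation".

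In analyses 2 and 3 the rule does not depend on arm, reason for stopping, covariates or time left to Week 96, and no exposure is added. SAP 4.4.1 lists no control-based, ocrelizumab-only or tipping-point analysis.

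On dropout itself, SAP 2.3 assumes about 20%, with no split by arm. Protocol 4.1.6.4 says that excluding patients in whom Rebif failed or was not tolerated "reduces the potential for unbalanced dropout rates". It gives no size or direction.

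**The concern.** An informative-dropout analysis should become harder to pass as the assumption about the experimental arm's dropouts worsens. A rule applied identically to both arms does not have that property. It penalises each arm in proportion to how many patients that arm loses, so the result turns on relative dropout and not on how badly ocrelizumab dropouts might have fared. If interferon loses enough additional patients, the more severe 100% rule gives a more favourable result than the primary analysis. A reader who sees both rules passed could then take this as evidence against a bias that neither rule was built to detect.

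**Working it through.** **Plan's own figure.** SAP 2.3 uses "two-sided tests with an experiment-wise alpha of 0.05", annualized rates of 0.165 (SD 0.60) and 0.33 (SD 0.80), and a relative reduction of 25% among dropouts. It states: "The sample size of 400 patients per treatment group provides 84% power, maintaining the type I error rate of 0.05".

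- Pooled SD = √((0.60² + 0.80²)/2) = 0.707
- Diluted difference = 0.8 × 0.165 + 0.2 × 0.25 × 0.33 = 0.1485
- Standard error = 0.707 × √(2/400) = 0.050
- Power = Φ(0.1485/0.050 − 1.96) = Φ(1.01) = 0.844

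This matches 84%. Without the dilution, power is Φ(0.165/0.050 − 1.96) = 0.910. So the sample size already assumes a weaker effect in dropouts and one dropout rate for both arms.

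**Effect of the rules on the rate ratio.** Let Ro and Ri be the observed rates and ao and ai the imputed relapses per patient-year. Then RR′ = (Ro + ao)/(Ri + ai), and RR′ < Ro/Ri exactly when ai/ao > 1/RR.

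For an arm with dropout d and fraction f imputed (0.5 or 1), a = f·d·(1 − R × 30/365.25) / [T(1 − d/2)], with T = 96 × 7/365.25 = 1.84 years. The factor f cancels from ai/ao, so both rules share one break-even point. Two inputs are assumptions outside the documents: the split of dropout by arm (average held at 20%) and dropouts leaving on average halfway through.

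Worked case, RR 0.50, 20% in each arm, 100% rule: ao = 0.2 × 0.986/1.656 = 0.119 and ai = 0.2 × 0.973/1.656 = 0.118, so RR′ = 0.284/0.448 = 0.64.

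| Dropout, ocrelizumab / interferon | RR′ from 0.50 (50% / 100% rule) | RR′ from 1.00 (50% / 100% rule) |
|---|---|---|
| 20 / 20 | 0.58 / 0.64 | 1.00 / 1.00 |
| 18 / 22 | 0.55 / 0.59 | 0.97 / 0.94 |
| 15 / 25 | 0.51 / 0.52 | 0.92 / 0.86 |
| 13.3 / 26.7 | 0.49 / 0.49 | 0.89 / 0.82 |
| 10 / 30 | 0.46 / 0.43 | 0.85 / 0.75 |

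**Break-even imbalance on the rate-ratio scale.**

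- RR 0.50: 13.8% vs 26.2%, or 1.9-fold (1.83 to 1.96 if dropouts leave on average at 25% to 75% of follow-up)
- RR 0.60: 15.4% vs 24.6%, or 1.6-fold
- RR 0.75: 17.4% vs 22.6%, or 1.3-fold
- RR 1.0: any interferon excess

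**Test statistic.** These are simulated negative binomial fits with 400 per arm, RR 0.50, an assumed dispersion of 1, and 169 to 184 usable fits per row. The last column adds events to ocrelizumab dropouts only, as a deliberately extreme bound.

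| Dropout | z, primary | z, planned 100% rule | RR and z, 100% rule in ocrelizumab only |
|---|---|---|---|
| 20 / 20 | −5.1 | −4.2 | 0.91, −0.8 |
| 18 / 22 | −4.9 | −4.9 | 0.88, −1.1 |
| 15 / 25 | −5.1 | −6.1 | 0.81, −1.8 |
| 13.3 / 26.7 | −5.0 | −6.7 | 0.77, −2.1 |

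The statistic therefore turns at about 18% vs 22%, a smaller imbalance than the ratio needs, because the added events also increase precision.

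**The case against.** The best defence is that the rules do challenge the result in the setting the trial was planned for. This stands: with equal or mildly unequal dropout the ratio moves towards 1, and even 10% vs 20% leaves 0.50 essentially unchanged (0.497 and 0.495). A reader might infer that any interferon excess tips the ratio towards ocrelizumab. That is true only when the underlying ratio is 1.

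The first of the three analyses imputes nothing and uses follow-up that discontinuers are asked to complete. This also stands, so the point cannot be extended to all the dropout sensitivity analyses. That analysis cannot, however, say what happened to patients who left the study.

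A reader might also infer that the rules could create a claimed benefit. With true rates of 0.33 in both arms and 10% vs 20% dropout, the ratio falls from 1.00 to 0.92 and 0.86. Taken alone, the chance of a significant result favouring ocrelizumab rises from about 3% to roughly 8–12% and 18–33% (robust Wald test, dispersion 1 to 4, the 50% rule run as a single draw). A negative binomial check of the 100% rule gave about 40%. But no claim rests on a sensitivity p-value: the testing hierarchy opens on the primary test, and joint significance with the primary stayed near 2%. These figures are not a trial error rate.

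The imbalance itself is assumed. The protocol describes mechanisms that could produce it, namely adverse reactions largely specific to interferon (2.1.5) and liver-enzyme stopping rules (5.6, 6.2.2). It predicts neither its direction nor its size.

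Finally, it is tempting to extend the point to Methods 1 and 2 for confirmed disability progression (SAP 4.4.2.3), which are also blind to arm. Under Method 2 a patient "will be imputed as an event of confirmed disability progression at the date of initial disability progression", but only after an observed initial progression, early discontinuation and no later EDSS. That resolves an observed, unconfirmed event and does not add one to dropouts in general. The effect has not been quantified, so no such claim is made.

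**Conclusion.** The point holds in limited form. The 50% and 100% rules measure sensitivity to relative dropout, and no analysis listed in SAP 4.4.1 asks what happens if ocrelizumab dropouts alone did worse. Whether the two rules attenuate or strengthen the result depends on the dropout split and the underlying ratio, with the break-even points shown above. Passing them is therefore not by itself evidence of robustness to informative dropout, though it is not worthless when dropout is similar between arms. The ocrelizumab-only bound shows that the gap can matter: at 20% dropout in each arm, z is −0.8 against −4.2 under the planned 100% rule.

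The sizes rest on an assumed split by arm, mid-period leaving times on average and, for the test statistics, dispersion 1. The break-even ratios vary little with leaving time. The primary analysis and the safety follow-up analysis are not affected.

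**What to change.** Keep both prespecified rules and report, beside them, the number of early discontinuers and of eligible patients in each arm. Add two analyses:

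- **Control-based multiple imputation.** Impute relapses from discontinuation to Week 96 from the fitted negative binomial model, using the interferon rate for dropouts in both arms, with exposure extended to Week 96.
- **Tipping point.** Using the same imputation, raise the relapse rate in ocrelizumab dropouts only, in steps, until significance is lost. Report the multiplier at which that happens. At the planned rates, a multiplier of 0.33/0.165 = 2 corresponds to the interferon rate and is a natural benchmark.

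These should be added and labelled post hoc, not substituted. SAP 2.4 lists the primary CSR as completed, and the January 2022 update was written after unblinding, so removing prespecified analyses now would be worse than the gap. The update already records other post-unblinding changes, and a final CSR is still planned. The cost is SAP wording, modest programming, and sensitivity results that will look less favourable than the current ones.

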4.4.2 Secondary Efficacy Endpoints

4.4.2.1 Rationale for Hierarchy of Secondary Efficacy Endpoints

The hierarchical order of secondary efficacy endpoints is shown below, with endpoints listed in descending order of importance. The rationale for this hierarchical order of secondary endpoints is based primarily on clinical meaningfulness (i.e., those endpoints that are clinically more meaningful are listed higher in the hierarchy). In situations where endpoints have similar clinical relevance, those endpoints with a greater chance of achieving a statistically significant treatment difference are listed higher in the hierarchy. Established, rather than novel, endpoints are generally given higher priority within the hierarchy.

For patients, reduction in disability progression is a highly meaningful clinical outcome, reflecting the degree to which they are able to maintain independence and quality of life.

The following is list of all secondary endpoints, also called key endpoints:

- The time to onset of confirmed disability progression for at least 12 weeks, with the initial event of neurological worsening occurring during the 96-week, double-blind, double-dummy treatment period is listed as the first secondary efficacy endpoint on the basis of its clinical meaningfulness.
- The second and third secondary efficacy endpoints listed in the hierarchy are MRI parameters (T1 Gd-enhancing lesions and new and/or enlarging T2 hyperintense lesions) that historically have shown to correlate well with the clinical course.
- The fourth secondary efficacy endpoint, disability improvement, is a clinical endpoint that, if achieved, would have even greater impact on the quality of life of patients than reduction in disability progression. However, it represents a novel endpoint. Therefore, this endpoint is placed lower within the hierarchy than the above endpoints.
- The fifth secondary efficacy endpoint is the time to onset of confirmed disability progression for at least 24 weeks, with the initial event of neurological worsening occurring during the 96-week, double-blind, double-dummy treatment period, but the modality being tested here (EDSS) is identical to that of the first secondary endpoint. Given that the number of 24-week CDP events will be lower than the number of 12 week CDP events, there is likely a lower chance of achieving a statistically significant treatment difference, and hence, the 24 week CDP is listed lower than the 12 week CDP. It is, however, listed relatively higher in the hierarchy as the fifth endpoint, given the greater clinical meaningfulness of disability progression than the remaining endpoints.
- The sixth and eighth secondary endpoints, chronic black holes and brain volume, are indicators of brain tissue loss. The possible correlation of such brain-atrophy measures and long-term clinical outcomes has been suggested in other studies ([Barkhof et al. 2009](#)). Therefore, because they are imaging modalities and the correlation to clinical outcomes is weaker than the imaging endpoints that are listed higher in the hierarchy, these endpoints are listed lower in the hierarchy than the clinical endpoints.
- The EDSS does not adequately assess upper limb function and cognitive impairment; therefore, the MSFC scale is used to address this gap in clinical disability assessment. However, since the MSFC scale is not as widely used in other studies and not as well-accepted as a validated endpoint, it is listed seventh in the hierarchy.
- The SF-36 is one of the most widely used and validated instruments for measuring quality of life in patients with MS. It is, however, listed as ninth in the hierarchy below all the other clinical measures because quality-of-life instruments in general are not as widely used in confirmatory clinical studies compared with the other clinical measures.

- The tenth and final secondary endpoint is a composite measure encompassing the absence of disease activity based on clinical and MRI parameters (i.e., consisting of the primary endpoint and secondary endpoints 1, 2, and 3 above). It is a highly meaningful endpoint for patients but is listed as last in the hierarchy because it is a combination of previous secondary endpoints.

4.4.2.2 Statistical Testing Strategy for Secondary Efficacy Endpoints

Secondary efficacy endpoints will be tested in the sequence presented in the hierarchical order listed in [Figure 1](#), all at the $\alpha=0.05$ level.

All p-values will be reported and will be interpreted as either confirmatory or non-confirmatory (i.e., descriptive only). The circumstances for confirmatory and for non-confirmatory interpretation of p-values are described below, and the sequence of the confirmatory tests is illustrated in [Figure 1](#).

The first secondary endpoint in the hierarchy is the time to onset of confirmed disability progression for at least 12 weeks with the initial event of neurological worsening occurring during the 96-week, double-blind, double-dummy treatment period, and the fifth secondary endpoint is the same, except progression is defined as sustained for at least 24 weeks during the 96-week comparative treatment period. The fourth secondary endpoint is the proportion of patients who have confirmed disability improvement for at least 12 weeks with the initial event of neurological improvement occurring during the 96-week, double-blind, double-dummy treatment. For these three endpoints, only when data from both Studies WA21092 and WA21093 are combined will there be sufficient statistical power to detect relevant treatment differences. For the other secondary efficacy endpoints and the primary efficacy endpoint (annualized protocol-defined relapse rate by 2 years), there is sufficient statistical power within each study to detect relevant treatment differences, without needing to combine data from the two studies.

As a consequence of this, for analyses of secondary efficacy endpoints at the individual study level:

- For the first secondary efficacy endpoint (the time to onset of confirmed disability progression for at least 12 weeks), the study-level p-value will be interpreted as non-confirmatory, due to inadequate statistical power at the study level to detect relevant treatment differences.
- The second secondary efficacy endpoint (total number of T1 Gd-enhancing lesions at Weeks 24, 48, and 96) will be tested in a confirmatory manner if and only if, in the analysis of both studies combined, the first secondary efficacy endpoint reaches a significance level of 0.05 (i.e., pooled analysis $p \leq 0.05$). If, in the analysis of the combined studies, the first secondary efficacy endpoint pooled analysis $p > 0.05$, then the second and subsequent secondary efficacy endpoint p-values within the hierarchy will be interpreted as non-confirmatory.
- The third secondary efficacy endpoint (total number of new and/or enlarging T2 hyperintense lesions at Weeks 24, 48, and 96) will be tested in a confirmatory manner if and only if the second secondary efficacy endpoint (total number of

T1 Gd-enhancing lesions at Weeks 24, 48, and 96) reaches a significance level of 0.05 (i.e., $p \leq 0.05$). If the second secondary efficacy endpoint $p > 0.05$, then the third and subsequent secondary efficacy endpoint p-values within the hierarchy will be interpreted as non-confirmatory.

- For the fourth (proportion of patients who have confirmed disability improvement for at least 12 weeks) and fifth (time to onset of confirmed disability progression for at least 24 weeks) secondary efficacy endpoints, the study-level p-value will be interpreted as non-confirmatory, due to inadequate statistical power at the study level to detect relevant treatment differences.
- The sixth secondary efficacy endpoint (total number of new T1-hypo-intense lesions (chronic black holes) at Weeks 24, 48, and 96) will be tested in a confirmatory manner if and only if, in the analysis of the combined studies, the fifth secondary efficacy endpoint (time to onset of confirmed disability progression for at least 12 weeks) reaches a significance level of 0.05 (i.e., pooled analysis $p \geq 0.05$). If, in the analysis of both studies combined, the fifth secondary efficacy endpoint pooled analysis $p > 0.05$, then the sixth and subsequent secondary efficacy endpoint p-values within the hierarchy will be interpreted as non-confirmatory.
- The seventh (and subsequent) secondary efficacy endpoint will be tested in a confirmatory manner if and only if the sixth (or immediately previous) secondary efficacy endpoint reaches a significance level of 0.05 (i.e., $p \leq 0.05$). If the sixth (or immediately previous) secondary efficacy endpoint $p > 0.05$, then the seventh (or current) and all subsequent secondary efficacy endpoint p-values within the hierarchy will be interpreted as non-confirmatory.

Furthermore, for analyses of secondary efficacy endpoints where data from both studies are combined (so there is sufficient statistical power for all primary and secondary efficacy endpoint comparisons):

[figure not shown]
- The first secondary efficacy endpoint (the time to onset of confirmed disability progression for at least 12 weeks) will be tested in a confirmatory manner if and only if the primary efficacy endpoint (annualized protocol-defined relapse rate by 2 years), reaches a significance level of 0.05 (i.e., pooled analysis $p \leq 0.05$). If the primary efficacy endpoint pooled analysis $p > 0.05$, then all secondary efficacy endpoint pooled analysis p-values within the hierarchy will be interpreted as non-confirmatory.
- The second (and subsequent) secondary efficacy endpoint will be tested in a confirmatory manner if and only if the first (or immediately previous) secondary efficacy endpoint reaches a significance level of 0.05 (i.e., pooled analysis $p \leq 0.05$). If the first (or immediately previous) secondary efficacy endpoint pooled analysis $p > 0.05$, then the second (or current) and all subsequent secondary efficacy endpoint pooled analysis p-values within the hierarchy will be interpreted as non-confirmatory.

The sequence of the confirmatory testing is illustrated in [Figure 1](#) below.

The arrows on the left illustrate the hierarchy of the statistical tests of Study WA21092. The arrows on the right illustrate the hierarchy of the statistical tests of Study WA21093. The boxes in the middle highlight the analyses performed in the pooled data set of WA21092 and WA21093.

For example, for Study WA21092, the primary endpoint ARR should be positive in both studies ($p \leq 0.05$). After the poolability of both Studies WA21092 and WA21093 has been observed (see more details in the Pooled SAP), the first secondary endpoint is tested in the pooled dataset WA21092 and WA21093. Then, the analysis of T1 Gd-enhancing lesions is performed for Study WA21092. If this is statistically significant ($p \leq 0.05$), the T2 hyperintense lesions are analyzed for Study WA21092. If this is statistically significant ($p \leq 0.05$), the analysis of confirmed disability improvement is done in the pooled data of Studies WA21092 and WA21093. If this is statistically significant ($p \leq 0.05$), then the analysis of Confirmed Disability Progression for at least 24 weeks is performed in the pooled data. If this is statistically significant ($p \leq 0.05$), the Chronic Black Holes endpoint is analyzed in Study WA21092. Then, the sequence of tests continues in the order of MSFC, brain volume, SF-36 PCS, and NEDA for Study WA21092.

Figure 1 Hierarchical Order of Key Efficacy Endpoints

ARR=annualized relapse rate; CDI=Confirmed Disability Improvement; CDP=confirmed disability progression; Gd=gadolinium; MSFC=Multiple Sclerosis Functional Composite Scale; NEDA=no evidence of disease activity; SF-36 PCS=short form 36 Physical Component Summary.

4.4.2.3 Time to Onset of Confirmed Disability Progression for at Least 12 Weeks with the Initial Event of Neurological Worsening Occurring during the 96-Week, Double-Blind, Double-Dummy Treatment Period

Disability progression as measured by EDSS will be assessed in all patients by the independent examining investigator at screening and baseline visit, and every 12 weeks throughout the study until the end of the double-blind, double-dummy treatment period at Week 96, after which disability progression is assessed at Weeks 12 and 24 in the OLE

and then every 24 weeks thereafter. Additional EDSS assessments for individual patients may be requested between visits (i.e., during an MS relapse).

Section 2.4 provides additional information on the timing of this analysis.

The EDSS is based on a standard neurological examination; the seven categories of the EDSS representing functional systems (Pyramidal, Cerebellar, Brainstem, Sensory, Bowel and Bladder, Visual, plus “Other”) are rated and scored (collectively, FSS). Each score of the FSS is an ordinal clinical rating scale ranging from 0 to 5 or 6. These ratings are then used in conjunction with observations and information concerning ambulation and use of assistive devices (which will also be scored) to determine the EDSS score. The EDSS is a disability scale that ranges in 0.5-point steps from 0 (normal) to 10.0 (death).

Because of the variability of EDSS, a single measurement at the baseline visit might not provide a sufficiently reliable baseline EDSS. Therefore, using an average score from two separate measurements may improve the reliability of baseline EDSS and the reliability of confirmed disability progression seen in the study. Inclusion criteria require neurological stability for 30 days prior to both screening and baseline visits. Generally, it takes 2 weeks for screening. There should be little change in EDSS except for the measurement variability during the screening period, assuming patients are clinically neurologically stable during this period.

In the derivation of time-to-onset confirmed-disability progression, baseline EDSS is defined as the average of the EDSS scores at the screening and baseline visits, without rounding.

Progression is defined a ≥ 1 -point increase in EDSS score from a baseline EDSS score of 0.0–5.5 inclusive, and a 0.5-increase from a baseline EDSS score higher than 5.5.

For example, for a patient with a baseline EDSS score of 5.25 or 5.5, the progression is defined as an EDSS score of at least 6.5. For a patient with a baseline EDSS score of 5.75 or 6.0, the progression is defined as an EDSS score of at least 6.5.

The inclusion criterion of EDSS (0–5.5) only applies to screening EDSS. Hence, it is still possible for a patient’s baseline EDSS score (derived from both screening and Day 1 EDSS results) to be >5.5 . Confirmation requires the sustained change in EDSS for at least 12 weeks from the initial progression. Initial progression can happen at any visit during the 96-week, double-blind, double-dummy treatment period.

Confirmation of disability progression must occur at the regularly scheduled visit that is at least 12 weeks (84 days) after initial progression. If a patient has a missing EDSS at the scheduled visit occurring at least 84 days after an initial progression or the scheduled visit occurs several days before the 84-day window after an initial progression

(e.g., the visit window is ± 4 days), confirmation of the disability progression must be on the basis of the assessment at the next scheduled visit. There may be EDSS assessments at unscheduled or scheduled visits that are < 84 days after the initial progression that are between the initial progression visit and the confirmation visit. Disability progression cannot be confirmed unless the EDSS values meet the minimum change required for progression. The non-confirmatory EDSS assessments (if any) between the initial disability progression and the confirmation of disability progression should be at least as high as the minimum change required for progression. All initial disability progression events up to Week 96 with corresponding confirmation visits at a subsequent scheduled visit will be taken into account for the statistical analysis, irrespective of whether the confirmation visit occurred during the treatment phase or in the SFU phase or OLE phase after study-drug discontinuation. Thus, patients who prematurely discontinue study drug treatment should remain in the SFU phase of the study, and every effort should be made to obtain a follow-up EDSS status at the next scheduled visit. Patients who, according to the above definition, did not have onset of confirmed disability progression by the Week-96 visit, by the time of the early discontinuation of treatment, or are lost to follow up will be censored at the date of the last EDSS assessment during the 96-week, double-blind, double-dummy treatment period.

Data from the two studies (with respect to the ocrelizumab group vs. the interferon beta-1a 44 μg SC group) will be pooled for analysis of this endpoint at the $\alpha=0.05$ level. Only data collected during the 96-week treatment period will be used for this analysis, although confirmation of disability progression during the 96-week, double-blind, double-dummy treatment period may occur during a subsequent study phase (i.e., during the SFU phase or the OLE phase).

Time to confirmed disability progression in the ocrelizumab group and in the interferon beta-1a 44 μg SC group will be compared using a two-sided log-rank test stratifying by geographical region (United States vs. ROW), and baseline EDSS (< 4.0 vs. ≥ 4.0). The proportion of patients with confirmed disability progression will be estimated using Kaplan-Meier methodology. A by-treatment Kaplan-Meier plot will be presented for this endpoint. The overall hazard ratio will be estimated using a stratified Cox regression model with treatment group as covariate and the same stratification factors used in the stratified log-rank test above.

Sample SAS code can be found below (SAS code is regarded as “draft” until fully validated at the analysis stage):

```
* Log-rank test;
proc lifetest data=CDP12;
  time CDP12TIME*CNSR(1);
  strata REGION BEDSSCAT / group=ARMCD;
  ods output HomTests =_logrank;
run;
```

```
* Cox regression model;
proc phreg data=CDP12;
```

```
class ARMCD / descending;  
model CDP12TIME*CNSR(1) = ARMCD / rl;  
strata REGION BEDSSCAT;  
ods output ParameterEstimates=est;  
run;
```

The analysis described above will be repeated for the per-protocol population as a sensitivity analysis.

Additionally, the following sensitivity analyses will be performed:

- Use of two different methods for handling of missing data:

Method 1: with use of the same kind of multiple imputation approach described at the end of Section 4.4.1, patients with an initial disability progression during the 96-week, double-blind, double-dummy treatment period who discontinue the treatment early and do not have a subsequent visit with EDSS measurement will be randomly imputed as an event of confirmed disability progression at the date of initial disability progression with a probability of 50%; the other 50% of these patients will be censored at the date of initial disability progression. A total of 1000 ($m=1000$) imputed datasets will be produced.

Method 2: Patients with an initial disability progression during the 96-week, double-blind, double-dummy treatment period who discontinue the treatment early and do not have a subsequent visit with EDSS measurement will be imputed as an event of confirmed disability progression at the date of initial disability progression.

- Adjustment for some additional baseline factors: Sensitivity analysis will use the same tests above but will, in addition, adjust for the number of relapses occurring within a 2-year period prior to study entry, baseline presence of Gd lesions (present or absent), prior MS treatment, and age (<40 vs. ≥ 40 years).

